3.2 Secondary Objectives and Endpoints

1. To evaluate the plasma concentration-time profile of nicotine and derived PK parameters (with and without adjustment for baseline nicotine concentrations) of the four P3P variants from the *ad libitum* use period.

Endpoints:

- Plasma nicotine concentration-time profile
- Peak plasma nicotine concentration [C_{peak}]
- Time to peak plasma nicotine concentration [t_{peak}]
- Trough plasma nicotine concentration [C_{trough}]
- Average of plasma nicotine concentration from T_0 ad lib to 1 hour [$C_{average}$]
- Area under the concentration-time curve from start of product use (T_0 ad lib) to 4 hours [$AUC_{ad\ lib\ (0-4h)}$]

2. To evaluate the pharmacodynamic effects (subjective effects and related behavioral assessments) of four P3P variants.

Endpoints:

- Visual Analogue Scale (VAS)-craving assessment from the fixed puffing regimen and *ad libitum* use period
- Product evaluation by an adapted version of the modified Cigarette Evaluation Questionnaire (adapted mCEQ) following the *ad libitum* use period
- Sensory Questionnaire (SQ) following the *ad libitum* use period

Confidentiality Statement

Data and information contained in this document are considered to constitute trade secrets and confidential commercial information, and the legal protections provided to such trade secrets and confidential information are hereby claimed under the provisions of applicable law. No part of this document may be publicly disclosed without the written consent of Philip Morris Products S.A.

3. To evaluate human puffing topography of four P3P variants during the fixed puffing regimen and the *ad libitum* use period.

Endpoints:

- Per-puff parameters and per-product use experience parameters

4. To estimate the amount of powder aerosolized from P3P from the fixed puffing regimen and the *ad libitum* use periods.

Endpoints:

- Weight difference of P3P before and after use

5. To monitor the safety and tolerability during the study.

Endpoints:

- Incidence of adverse events (AEs), serious adverse events (SAEs)
- Frequency of AEs, SAEs
- Incidence of P3P product events including malfunction/misuse
- Frequency of P3P product events including malfunction/misuse
- Physical examination changes from baseline
- Cough changes from baseline (VAS and three Likert scales)
- Electrocardiogram (ECG) changes from baseline (heart rate, PR, QRS, QT, QTcB, QTcF intervals)

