9 STUDY ACTIVITIES

A detailed schedule of all study activities and assessments is provided in Appendix A. Measurements not conducted at the exact time point indicated, but conducted within the given time window (if applicable) do not constitute a protocol deviation but an accepted variability for the given time point.

In general, if no start time for the procedure is provided, then the procedure can be performed at any time during the day.

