Time	Blood Sample	Procedures	Additional Information
Start of Procedure			
Prior to product use (within 2 hours)		Assembly and weighing of products for ad libitum use	
15 ± 5 minutes prior to T_0 ad lib	✓	Blood sampling for baseline nicotine level for ad libitum use	
15 ± 5 minutes prior to T_0 ad lib		VAS-craving: baseline for ad libitum use	
Just before each product use		Piercing of P3P capsule	

Confidentiality Statement

Data and information contained in this document are considered to constitute trade secrets and confidential commercial information, and the legal protections provided to such trade secrets and confidential information are hereby claimed under the provisions of applicable law. No part of this document may be publicly disclosed without the written consent of Philip Morris Products S.A.

Time	Blood Sample	Procedures	Additional Information
Start of Procedure			
Start of product use: T _{0 ad lib}		Product use (ad libitum for 1 hour) with HPT recording	After at least 10 hours of nicotine washout. At each day the same product which is used for fixed puffing in the morning will be used for the 1 hour ad libitum session in the afternoon.
During/after ad libitum product use	✓	Blood sampling for nicotine PK assessment from the ad libitum use	Post T _{0 ad lib} , blood will be drawn at the following time points: T1 after 10 minutes ± 1 minute, T2 after 20 minutes ± 2 minutes, T3 after 30 minutes ± 2 minutes, T4 after 40 minutes ± 5 minutes, T5 after 1 hour ± 5 minutes, T6 after 2 hours ± 5 minutes, T7 after 4 hours ± 5 minutes.
During/after ad libitum product use		VAS-craving	Post T _{0 ad lib} , craving will be assessed at the following time points 10 minutes (± 2 minutes) 20 minutes (± 2 minutes) 30 minutes (± 5 minutes) 40 minutes (± 5 minutes) 1 hour (± 10 minutes) 2 hours (± 10 minutes) 4 hours (± 10 minutes)
Within 75 min after start of product use (T _{0 ad lib})		Collection and weighing of used products	
Within 60 minutes after the end of ad libitum product use		Adapted mCEQ	
Within 60 minutes after the end of ad libitum product use		Sensory Questionnaire	
60 ± 10 minutes after the end of ad libitum product use		Vital signs (blood pressure, pulse rate, respiratory rate)	At least 5 min in supine position prior to measurement.

Confidentiality Statement

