### 7.1.2 PK Parameters

For PK parameters, baseline is defined in Section 4.1 "Definitions for Statistical Analysis".

To minimize the carry-over effect in the nicotine plasma PK parameters due to limited washout periods, background-concentration correction will be applied to the concentration data for the fixed puffing regimen and *ad libitum* use. The baseline correction will be implemented by calculating the nicotine exposure parameters using adjusted concentration values. The plasma nicotine background-correction methodology will be confirmed following the conduct of an interim analysis as described in Section 13.1.3 "Interim Analysis Methods".

Nicotine PK parameters will be derived from both measured plasma nicotine concentrations, as well as the background-corrected plasma nicotine concentrations using noncompartmental analysis principles.

The actual blood sampling times post-exposure collected in the CRF will be used in the computation of the PK parameters, with the exception of pre-exposure sampling time which will be considered as time zero ( $T_0$  fix or  $T_0$  ad lib).

PK parameters for the fixed regimen use will be derived using the nicotine concentration assessed between  $T_0$  fix and the last available timepoint of the fixed regimen (4h±30min after product use). For the calculation of the AUC only, the window can be extended up to the pre-dose nicotine concentration before the *ad libitum* use.

PK parameters for the *ad libitum* use will be derived using the nicotine concentration assessed between  $T_0$  ad lib and the last available timepoint of *ad libitum* use (4h±30 min after first product use). For the calculation of the AUC only, the window can be extended up to the pre-dose nicotine concentration before the next fixed regimen use or, in the last period only, to the additional samples collected.

The following PK parameters will be calculated, as per protocol background-corrected PK endpoints, for the fixed (Table 2) and *ad libitum* (Table 3) regimens.

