**Table 3 Background-corrected Ad Libitum Regimen Nicotine Plasma PK Parameters**

Parameter	Definition
$cC_{peak}$	Background-corrected peak plasma nicotine concentration
$c_{t_{peak}}$	Time to peak plasma nicotine background-corrected concentration during ad libitum use, $c_{t_{peak}}$ will be reported as long as there is at least one quantifiable concentration post-exposure
$cAUC_{ad\ lib(0-4h)}$	Area under the concentration-time curve from start of product use ( $T_0_{ad\ lib}$ ) to 4 hours
$cC_{trough}$	Background-corrected trough plasma nicotine concentration from $T_0_{ad\ lib}$ to 1 hour
$cC_{average}^a$	Background-corrected average of plasma nicotine concentration from $T_0_{ad\ lib}$ to 1 hour

a  $cC_{average}$  is calculated by estimating the area under the concentration-time curve using background-corrected nicotine concentrations from the start of product use up to the last available concentration within 1 hour post product use, divided by the collection interval

Uncorrected PK parameters will also be presented, and the corresponding estimated PK parameters are described in Table 4, for the fixed regimens, and in Table 5, for the *ad libitum* regimens.

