**Table 5 Ad Libitum Regimen Nicotine Plasma PK Parameters (Uncorrected)**

Parameter	Definition
$C_{\text{peak}}$	Peak plasma nicotine concentration
$AUC_{\text{ad lib}(0-4h)}$	Area under the concentration-time curve from start of product use ( $T_0 \text{ ad lib}$ ) to 4 hours
$t_{\text{peak}}$	Time to peak plasma nicotine concentration during ad libitum use, $t_{\text{peak}}$ will be reported as long as there is at least one quantifiable concentration post-exposure
$C_{\text{trough}}$	Trough plasma nicotine concentration after from $T_0 \text{ ad lib}$ to 1 hour
$C_{\text{average}}^a$	Average of plasma nicotine concentration from $T_0 \text{ ad lib}$ to 1 hour

a  $C_{\text{average}}$  is calculated by estimating the area under the concentration-time curve from the start of product use up to the last available concentration within 1 hour post product use, divided by the collection interval

In addition,  $\lambda_z$ -related nicotine plasma PK parameters will be calculated following the last product use (Days 4 to 5), as shown in Table 6:

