### 7.1.2.2 Calculation of AUC

The minimum requirement for the calculation of the *ad libitum* or fixed AUC(0-4h) is the inclusion of at least 3 plasma concentrations above the lower limit of quantitation (LLOQ), with at least 1 of these concentrations following Cmax. For the *ad libitum* use, cases where Cmax is achieved at 4 hours will be evaluated on individual basis.

The AUC will be set to missing if the last available concentration before 4 hours is not on the terminal phase of the individual time-concentration curve (as assessed by the goodness of fit criteria defined in section 7.1.2.3) otherwise the first available concentration after 4 hours and before the next product use will be used for interpolating the concentration value at 4 hours for the fixed regimen use.

A similar approach will be used for the *ad libitum* use with the exception of the last period (day 4), where the first available concentration after 4 hours will be used for interpolating the concentration value at 4 hours.

The corresponding total exposure parameters or AUCs (e.g. cAUCfix(0-4h), cAUCad lib(0-4h), etc.) will be calculated following the conventional linear trapezoidal method.

The same approach will be applied for the corresponding baseline corrected PK parameters by using the nicotine concentration adjusted for baseline.

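### The rule for C_average and cC_average drops a compliant 1 h sample drawn at 61–65 min, so the stated 0–1 h average can become an average over about 0–40 min

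*SAP*

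**What the plan says.** - **Endpoint.** Protocol Section 3.2 defines C_average as "Average of plasma nicotine concentration from T_0 ad lib to 1 hour". SAP Section 5.2 and the parameter definitions in SAP Tables 3 and 5 use the same interval.
- **Computation.** The Table 3 footnote (background-corrected) takes the area "up to the last available concentration within 1 hour post product use, divided by the collection interval". The Table 5 footnote (uncorrected) has the same rule: "from the start of product use up to the last available concentration within 1 hour post product use, divided by the collection interval".
- **Time basis.** SAP Section 7.1.2: "The actual blood sampling times post-exposure collected in the CRF will be used in the computation of the PK parameters". The pre-use sample is set to time zero.
- **Sampling.** Protocol Table 10 (Section 9.3) schedules "T4 after 40 minutes ± 5 minutes, T5 after 1 hour ± 5 minutes, T6 after 2 hours ± 5 minutes", and SAP Table 16 has the same windows. The 1 h draw may therefore fall at 55–65 min, and the draw before it at 35–45 min.
- **Status of an off-nominal draw.** Protocol Section 9 says measurements made inside their window "do not constitute a protocol deviation but an accepted variability for the given time point".
- **The same issue at 4 h.** For AUC(0–4h), SAP Section 7.1.2.2 says that "the first available concentration after 4 hours and before the next product use will be used for interpolating the concentration value at 4 hours". No such rule is given at 1 h.

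**The concern.** Taken together, these rules exclude a sample that the protocol accepts. A T5 draw at 61 min is in window, but its actual time is not within 1 hour. The area then ends at T4 and is divided by about 40 min. Dividing by the shorter interval does not repair this, because it gives the mean of an earlier window. If concentrations are still rising, that mean is lower. A minute of clock time decides which quantity a subject contributes, and the plan neither flags such a profile nor sets it to missing.

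Both versions of the parameter are summarized by variant. They are also analysed on the log scale, with geometric mean ratios and 95% CIs overall and by sex (SAP Section 12.6.2.1). A mixture of 0–1 h and 0–40 min averages lowers the reported levels and adds scatter that has nothing to do with the product. With 18 randomized subjects, a chance imbalance in late draws between variants is also possible.

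**Working it through.** The plan states no figure that depends on C_average, so there is none to reproduce. The check sizes the error when T5 is dropped.

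**Inputs from the documents.** Sampling times and windows as above; half-lives of 1.35 h (initial) and 17 h (terminal), Protocol Section 4.2. **Assumed, because not given:** the use pattern (Protocol Section 6.2.2 leaves it unrestricted) and the distribution of draw times within the window.

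**1. Straight-line rise from zero, slope s per minute.** Mean over 0–40 min = 20s; mean over 0–60 min = 30s. Ratio 20/30 = 0.667, so −33%.

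**2. Constant-rate use for 60 min, 1.35 h half-life, zero baseline (cC_average).** C(t) = A(1 − e^(−kt)), with k = ln 2/1.35 = 0.513 per h. Mean over 0–T = A[1 − (1 − e^(−kT))/(kT)].
- T = 2/3 h: 0.1532A
- T = 1 h: 0.2179A
- Ratio 0.703, so −30%. The trapezoid on the scheduled times also gives −30%.
- With T4 itself drawn at 35 or 45 min: −38% or −22%.

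**3. Other use patterns** (trapezoid; fast-phase fraction 1.0, 0.9 or 0.7 assumed):

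| Use pattern | Error if T5 is dropped |
|---|---|
| Constant over 60 min | −30% to −31% |
| Two products, at 0 and 30 min | −21% to −22% |
| Three products, at 0, 20 and 40 min | −20% to −22% |
| 70% of use in first 30 min | −20% to −22% |
| Use only in 0–30 min | −10% to −12% |
| Use only in 0–20 min | −3% to −5% |
| One product at the start | +1% to +3% |
| One product, at 50–56 min only | −100% |

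**4. Uncorrected C_average, constant use.** Add a baseline of b times the 60-minute rise (0.4016A), decaying with the 17 h half-life. Its mean level is 0.9865 of the start over 40 min and 0.9799 over 60 min.
- b = 1: (0.3962 + 0.1532)/(0.3935 + 0.2179) = 0.899, so −10%.
- b = 0.1: (0.0396 + 0.1532)/(0.0394 + 0.2179) = 0.749, so −25%.
- b = 0.5 and 0.25 give −15% and −20%.

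**5. Share of profiles with T5 after 60 min** (a draw recorded as exactly 60 min counts as within 1 hour):

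| Assumed draw times, 55–65 min | Share late |
|---|---|
| Continuous, symmetric about 60 | 50% |
| Uniform on whole minutes | 5/11 = 45% |
| Normal, mean 60, SD 1–2, recorded to the minute | 31–40% |
| Normal, mean 58–59, SD 2, recorded to the minute | 11–23% |
| Normal, mean 61–62, SD 2, recorded to the minute | 59–76% |

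With 18 × 4 = 72 profiles, 11% to 76% is about 8 to 55.

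**6. Effect on the analysis if half the profiles are affected at −30%.** The log shift is ln 0.703 = −0.352. The geometric mean changes by e^(0.5 × −0.352) − 1 = −16%. Added log-scale SD = 0.352 × √(0.5 × 0.5) = 0.176. At an assumed within-subject log SD of 0.3, the standard error of a ratio rises by √((0.090 + 0.031)/0.090) = 1.16, about 16%, provided lateness is independent from day to day.

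**7. Check of the remedy.** With T5 at 65 min and interpolation from T4–T5 to 60 min, the error against the 0–60 min value is about −3% to 0% over the patterns in step 3, except −22% to −23% for a single product at 50–56 min. With constant use and T5 at 55 min, interpolation from T5–T6 gives about −0.6%.

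**The case against.** The strongest reply is that *within 1 hour* means the nominal 1 h time point, so T5 always counts. There is support for it:
- The abbreviation lists in both documents describe C_average as the average during the ad libitum period, which lasts 60 ± 5 min.
- Protocol Section 9 treats an in-window draw as belonging to its time point.
- SAP Section 7.1.2 gives the end of the PK interval as a time point with a tolerance.
- Dividing by the collection interval also fits using T5 at its actual time.

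On that reading no sample is lost, and the residual error is about −7% (T5 at 55 min) to +7% (T5 at 65 min) with steady use.

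The reading is possible, but the SAP does not state it. Section 7.1.2 specifies actual times, and Section 12.1.5 falls back on nominal times only when an actual time is missing. Two programmers could derive different values from the same data.

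Three further replies stand and limit the point. Draw-time noise unrelated to variant does not bias the ratios on average. If a subject tends to be drawn late on every day, much of it cancels within subject. The study tests no hypothesis, and SAP Section 12.1.8 says no claim rests on individual intervals.

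A reader might infer that about half of all profiles will read about 30% low. The documents do not support that. It needs draws symmetric about 60 min and finely recorded, steady use for the whole hour, and a zero baseline, none of which they give.

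**Conclusion.** The point holds as a fault in the derivation rule. On its literal terms, a compliant T5 draw at 61–65 min is excluded, and the parameter is no longer the 0–1 h average that both documents define. The SAP deals with the matching problem at 4 h but not at 1 h.

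The size is a range. The share of affected profiles is about 11% to 76% under the timings tried. In an affected profile, cC_average is about 30% low with steady use, about 20–22% low with spaced or front-loaded use, and within a few per cent if use is confined to the start. A single product used only after 40 min is the extreme case, since its contribution is lost entirely. Uncorrected C_average is about 10–25% low with steady use, depending on baseline.

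Absolute levels are biased. Variant ratios are not biased on average if late draws are equally common across variants, but their confidence intervals widen. The amendment is worth making before the derivation is run. The primary endpoints are not touched.

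**What to change.** In the footnotes to SAP Tables 3 and 5, state that:
- the T5 sample is used at its actual in-window time, including when that is after 60 min;
- the concentration at exactly 60 min is obtained by linear interpolation, between T4 and T5 if T5 is late and between T5 and T6 if T5 is early, in line with the 4 h rule in SAP Section 7.1.2.2;
- the area from T0 ad lib to 60 min is divided by 1 h.

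Add that T5 also counts as inside the 0–1 h interval for C_trough and cC_trough, whose definitions in the same tables leave the same doubt.

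The cost is two footnotes and one derivation step. All the samples needed are already scheduled and their actual times are recorded, so no new data are required.

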**Table 4 Fixed Regimen Nicotine Plasma PK Parameters (Uncorrected)**

Parameter	Definition
$C_{\max}$	Maximum observed plasma concentration.
$t_{\max}$	Time of maximum observed plasma concentration.
$AUC_{fix(0-4h)}$	Area under the concentration-time curve from start of product use ( $T_0_{fix}$ ) to 4 hours

**Table 5 Ad Libitum Regimen Nicotine Plasma PK Parameters (Uncorrected)**

Parameter	Definition
-----------	------------

**Table 5 Ad Libitum Regimen Nicotine Plasma PK Parameters (Uncorrected)**

Parameter	Definition
$C_{\text{peak}}$	Peak plasma nicotine concentration
$AUC_{\text{ad lib}(0-4h)}$	Area under the concentration-time curve from start of product use ( $T_0 \text{ ad lib}$ ) to 4 hours
$t_{\text{peak}}$	Time to peak plasma nicotine concentration during ad libitum use, $t_{\text{peak}}$ will be reported as long as there is at least one quantifiable concentration post-exposure
$C_{\text{trough}}$	Trough plasma nicotine concentration after from $T_0 \text{ ad lib}$ to 1 hour
$C_{\text{average}}^a$	Average of plasma nicotine concentration from $T_0 \text{ ad lib}$ to 1 hour

a  $C_{\text{average}}$  is calculated by estimating the area under the concentration-time curve from the start of product use up to the last available concentration within 1 hour post product use, divided by the collection interval

In addition,  $\lambda_z$ -related nicotine plasma PK parameters will be calculated following the last product use (Days 4 to 5), as shown in Table 6:

**Table 6 Nicotine  $\lambda_z$ -related Parameters Following Last P3P Product Use (Days 4 to 5)**

Parameter	Definition
Adjusted-R 	Adjusted coefficient of determination for the terminal elimination phase, adjusted for the number of points used in the estimation of $\lambda_z$ .
No. points $\lambda_z$	Number of points used in computing $\lambda_z$ . If $\lambda_z$ cannot be estimated, zero.
$\lambda_z$ upper	Upper timepoint included in the calculation of $\lambda_z$ .
$\lambda_z$ lower	Lower timepoint included in the calculation of $\lambda_z$ .
$\lambda_z$	Terminal elimination rate constant, estimated by linear regression analysis of the natural log-transformed concentration-time data
$t_{1/2z}$	Terminal elimination half-life

Additional PK parameters may be determined in order to support the interpretation where appropriate.

### 7.1.2.1 Calculation of $C_{\text{max}}$ , $t_{\text{max}}$ , $C_{\text{peak}}$ , $t_{\text{peak}}$ with and without baseline adjustment

The minimum requirement for the determination of the  $C_{\text{max}}$  is the inclusion of at least one quantifiable concentration within 1 hour post-exposure.  $C_{\text{max}}$ ,  $t_{\text{max}}$ ,  $C_{\text{peak}}$ ,  $t_{\text{peak}}$  will be obtained directly from the plasma concentration-time profiles. If  $C_{\text{max}}$  (respectively  $C_{\text{peak}}$ ) occurs at more than one time point,  $t_{\text{max}}$  (respectively  $t_{\text{peak}}$ ) will be assigned to the first occurrence of the  $C_{\text{max}}$  (respectively  $C_{\text{peak}}$ ).

#### Confidentiality Statement

Data and information contained in this document are considered to constitute trade secrets and confidential commercial information, and the legal protections provided to such trade secrets and confidential information are hereby claimed under the provisions of applicable law. No part of this document may be publicly disclosed without the written consent of Philip Morris Products S.A.

The same approach will be applied for the corresponding baseline corrected PK parameters by using the nicotine concentration adjusted for baseline.

### 7.1.2.2 Calculation of AUC

The minimum requirement for the calculation of the *ad libitum* or fixed AUC(0-4h) is the inclusion of at least 3 plasma concentrations above the lower limit of quantitation (LLOQ), with at least 1 of these concentrations following Cmax. For the *ad libitum* use, cases where Cmax is achieved at 4 hours will be evaluated on individual basis.

The AUC will be set to missing if the last available concentration before 4 hours is not on the terminal phase of the individual time-concentration curve (as assessed by the goodness of fit criteria defined in section 7.1.2.3) otherwise the first available concentration after 4 hours and before the next product use will be used for interpolating the concentration value at 4 hours for the fixed regimen use.

A similar approach will be used for the *ad libitum* use with the exception of the last period (day 4), where the first available concentration after 4 hours will be used for interpolating the concentration value at 4 hours.

The corresponding total exposure parameters or AUCs (e.g. cAUCfix(0-4h), cAUCad lib(0-4h), etc.) will be calculated following the conventional linear trapezoidal method.

The same approach will be applied for the corresponding baseline corrected PK parameters by using the nicotine concentration adjusted for baseline.

